Parameter	Grade 1 (Mild)	Grade 2 (Moderate)	Grade 3 (Severe)	Grade 4 (Potentially Life-Threatening)
Site Reactions to Injections and Infusions (cont.)^f				
Injection-site pruritus ^f	Itching localized to the injection site that is relieved spontaneously or requires treatment for <48 hours	Itching beyond the injection site that is not generalized or itching localized to the injection site that requires treatment for ≥48 hours	Generalized itching causing inability to perform usual social and functional activities	—
Chemistries				
Acidosis	—	pH ≥ 7.3 to < LLN	pH < 7.3 without life-threatening consequences	pH < 7.3 with life-threatening consequences
Albumin, low	3.0 g/dL to < LLN (30 g/L to < LLN)	≥ 2.0 to < 3.0 g/dL (≥ 20 to < 30 g/L)	< 2.0 g/dL (< 20 g/L)	—
Alkaline phosphatase, high	1.25 to < 2.5 × ULN	2.5 to < 5.0 × ULN	5.0 to < 10.0 × ULN	≥ 10.0 × ULN
Alkalosis	—	pH > ULN to ≤ 7.5	pH > 7.5 without life-threatening consequences	pH > 7.5 with life-threatening consequences
ALT or SGPT, high (Report the most appropriate term)	1.25 to < 2.5 × ULN	2.5 to < 5.0 × ULN	5.0 to < 10.0 × ULN	≥ 10.0 × ULN
Amylase (pancreatic) or amylase (total), high (Report the most appropriate term)	1.1 to < 1.5 × ULN	1.5 to < 3.0 × ULN	3.0 to < 5.0 × ULN	≥ 5.0 × ULN

LLN = lower limit of normal; ULN = upper limit of normal.

^f Refer to Section 5.3.5.1 for instructions on reporting injection-site reactions to study treatment (if applicable). For reactions to drugs other than study treatment, report the most appropriate term and report multiple events, if applicable.

Appendix 10: Division of AIDS (DAIDS) Table for Grading the Severity of Adult and Pediatric Adverse Events

Table 1 Severity Grading for Adult and Pediatric Adverse Events (cont.)

Parameter	Grade 1 (Mild)	Grade 2 (Moderate)	Grade 3 (Severe)	Grade 4 (Potentially Life-Threatening)
Chemistries (cont.)				
AST or SGOT, high (Report the most appropriate term)	1.25 to $<2.5 \times$ ULN	2.5 to $<5.0 \times$ ULN	5.0 to $<10.0 \times$ ULN	$\geq 10.0 \times$ ULN
Bicarbonate, low	16.0 mEq/L to $<$ LLN (16.0 mmol/L to $<$ LLN)	11.0 to <16.0 mEq/L (11.0 to <16.0 mmol/L)	8.0 to <11.0 mEq/L (8.0 to <11.0 mmol/L)	<8.0 mEq/L (<8.0 mmol/L)
Bilirubin (direct), high: >28 days of age	—	—	>ULN with other signs and symptoms of hepatotoxicity	>ULN with life-threatening consequences (e.g., signs and symptoms of liver failure)
Bilirubin (direct), high: ≤ 28 days of age	ULN to ≤ 1 mg/dL	>1 to ≤ 1.5 mg/dL	>1.5 to ≤ 2 mg/dL ^h	>2 mg/dL ^h
Bilirubin (total), high: >28 days of age	1.1 to $<1.6 \times$ ULN	1.6 to $<2.6 \times$ ULN	2.6 to $<5.0 \times$ ULN	$\geq 5.0 \times$ ULN
Bilirubin (total), high: ≤ 28 days of age	See Table 7			
Calcium, high: ≥ 7 days of age	10.6 to <11.5 mg/dL (2.65 to <2.88 mmol/L)	11.5 to <12.5 mg/dL (2.88 to <3.13 mmol/L)	12.5 to <13.5 mg/dL (3.13 to <3.38 mmol/L)	≥ 13.5 mg/dL (≥ 3.38 mmol/L)
Calcium, high: < 7 days of age	11.5 to <12.4 mg/dL (2.88 to <3.10 mmol/L)	12.4 to <12.9 mg/dL (3.10 to <3.23 mmol/L)	12.9 to <13.5 mg/dL (3.23 to <3.38 mmol/L)	≥ 13.5 mg/dL (≥ 3.38 mmol/L)
Calcium (ionized), high	>ULN to <6.0 mg/dL ($>$ ULN to <1.5 mmol/L)	6.0 to <6.4 mg/dL (1.5 to <1.6 mmol/L)	6.4 to <7.2 mg/dL (1.6 to <1.8 mmol/L)	≥ 7.2 mg/dL (≥ 1.8 mmol/L)

LLN = lower limit of normal; ULN = upper limit of normal.

^h Direct bilirubin >1.5 mg/dL in a participant ≤ 28 days of age should be graded as Grade 2, if $<10\%$ of the total bilirubin.

Appendix 10: Division of AIDS (DAIDS) Table for Grading the Severity of Adult and Pediatric Adverse Events

Table 1 Severity Grading for Adult and Pediatric Adverse Events (cont.)

Parameter	Grade 1 (Mild)	Grade 2 (Moderate)	Grade 3 (Severe)	Grade 4 (Potentially Life-Threatening)
Chemistries (cont.)				
Calcium, low: ≥ 7 days of age	7.8 to <8.4 mg/dL (1.95 to <2.10 mmol/L)	7.0 to <7.8 mg/dL (1.75 to <1.95 mmol/L)	6.1 to <7.0 mg/dL (1.53 to <1.75 mmol/L)	<6.1 mg/dL
Calcium, low: < 7 days of age	6.5 to <7.5 mg/dL (1.63 to <1.88 mmol/L)	6.0 to <6.5 mg/dL (1.50 to <1.63 mmol/L)	5.50 to <6.0 mg/dL (1.38 to <1.50 mmol/L)	<5.50 mg/dL
Calcium (ionized), low	<LLN to 4.0 mg/dL 3.6 to <4.0 mg/dL (0.9 to <1.0 mmol/L)	3.2 to <3.6 mg/dL (0.8 to <0.9 mmol/L)	<3.2 mg/dL<br (<0.8="" l)<="" mmol="" td=""/>	3.6 to <4.0 mg/dL (0.9 to <1.0 mmol/L)	3.2 to <3.6 mg/dL (0.8 to <0.9 mmol/L)	<3.2 mg/dL
Cardiac troponin I, high	—	—	—	Levels consistent with myocardial infarction or unstable angina as defined by the local laboratory
Creatine kinase, high	3 to <6 × ULN	6 to <10 × ULN	10 to <20 × ULN	≥20 × ULN
Creatinine, high	1.1 to 1.3 × ULN	>1.3 to 1.8 × ULN or increase to 1.3 to <1.5 × baseline ⁱ	>1.8 to <3.5 × ULN or increase to 1.5 to <2.0 × baseline ⁱ	≥3.5 × ULN or increase to ≥2.0 × baseline ⁱ
Creatinine clearance or eGFR, low (Report the most appropriate term)	—	<90 to 60 mL/min or mL/min/1.73 m ² or 10% to <30% decrease from baseline ^j	<60 to 30 mL/min or mL/min/1.73 m ² or 30% to <50% decrease from baseline ^j	<30 mL/min or mL/min/1.73 m ² or ≥50% decrease from baseline ^j or dialysis needed

eGFR = estimated glomerular filtration rate; LLN = lower limit of normal; ULN = upper limit of normal.

ⁱ For participant with normal baseline value, grade should be based on current value relative to ULN. For participant with elevated baseline value, grade should be based on current value relative to baseline value.

^j For participant with normal baseline value, grade should be based on current value. For participant with elevated baseline value, grade should be based on current value relative to baseline value.

Appendix 10: Division of AIDS (DAIDS) Table for Grading the Severity of Adult and Pediatric Adverse Events

Table 1 Severity Grading for Adult and Pediatric Adverse Events (cont.)

Parameter	Grade 1 (Mild)	Grade 2 (Moderate)	Grade 3 (Severe)	Grade 4 (Potentially Life-Threatening)
Chemistries (cont.)				
Glucose (fasting), high	110 to 125 mg/dL (6.11 to < 6.95 mmol/L)	> 125 to 250 mg/dL (6.95 to < 13.89 mmol/L)	> 250 to 500 mg/dL (13.89 to < 27.75 mmol/L)	≥ 500 mg/dL (≥ 27.75 mmol/L)
Glucose (non-fasting), high	116 to 160 mg/dL (6.44 to < 8.89 mmol/L)	> 160 to 250 mg/dL (8.89 to < 13.89 mmol/L)	> 250 to 500 mg/dL (13.89 to < 27.75 mmol/L)	≥ 500 mg/dL (≥ 27.75 mmol/L)
Glucose, low: ≥ 28 days of age	55 to 64 mg/dL (3.05 to < 3.55 mmol/L)	40 to < 55 mg/dL (2.22 to < 3.05 mmol/L)	30 to < 40 mg/dL (1.67 to < 2.22 mmol/L)	< 30 mg/dL (< 1.67 mmol/L)
Glucose, low: < 28 days of age	50 to 54 mg/dL (2.78 to < 3.00 mmol/L)	40 to < 50 mg/dL (2.22 to < 2.78 mmol/L)	30 to < 40 mg/dL (1.67 to < 2.22 mmol/L)	< 30 mg/dL (< 1.67 mmol/L)
Lactate, high	ULN to < 2.0 × ULN without acidosis	≥ 2.0 × ULN without acidosis	Increased lactate with pH < 7.3 without life-threatening consequences	Increased lactate with pH < 7.3 with life-threatening consequences
Lipase, high	1.1 to < 1.5 × ULN	1.5 to < 3.0 × ULN	3.0 to < 5.0 × ULN	≥ 5.0 × ULN
Lipid disorder: cholesterol (fasting), high: ≥ 18 years of age	200 to < 240 mg/dL (5.18 to < 6.19 mmol/L)	240 to < 300 mg/dL (6.19 to < 7.77 mmol/L)	≥ 300 mg/dL (≥ 7.77 mmol/L)	—
Lipid disorder: cholesterol (fasting), high: < 18 years of age	170 to < 200 mg/dL (4.40 to < 5.15 mmol/L)	200 to < 300 mg/dL (5.15 to < 7.77 mmol/L)	≥ 300 mg/dL (≥ 7.77 mmol/L)	—
Lipid disorder: LDL (fasting), high: ≥ 18 years of age	130 to < 160 mg/dL (3.37 to < 4.12 mmol/L)	160 to < 190 mg/dL (4.12 to < 4.90 mmol/L)	≥ 190 mg/dL (≥ 4.90 mmol/L)	—

ULN=upper limit of normal.

Appendix 10: Division of AIDS (DAIDS) Table for Grading the Severity of Adult and Pediatric Adverse Events

Table 1 Severity Grading for Adult and Pediatric Adverse Events (cont.)

Parameter	Grade 1 (Mild)	Grade 2 (Moderate)	Grade 3 (Severe)	Grade 4 (Potentially Life-Threatening)
Chemistries (cont.)				
Lipid disorder: LDL (fasting), high: >2 to <18 years of age	110 to <130 mg/dL (2.85 to <3.34 mmol/L)	130 to <190 mg/dL (3.34 to <4.90 mmol/L)	≥190 mg/dL (≥4.90 mmol/L)	—
Lipid disorder: triglycerides (fasting), high	150 to 300 mg/dL (1.71 to 3.42 mmol/L)	>300 to 500 mg/dL (>3.42 to 5.7 mmol/L)	>500 to <1,000 mg/dL (>5.7 to 11.4 mmol/L)	>1,000 mg/dL (>11.4 mmol/L)
Magnesium, low	1.2 to <1.4 mEq/L (0.60 to <0.70 mmol/L)	0.9 to <1.2 mEq/L (0.45 to <0.60 mmol/L)	0.6 to <0.9 mEq/L (0.30 to <0.45 mmol/L)	<0.6 mEq/L (<0.30 mmol/L)
Phosphate, low: >14 years of age	2.0 mg/dL to <LLN (0.65 mmol/L to <LLN)	1.4 to <2.0 mg/dL (0.45 to <0.65 mmol/L)	1.0 to <1.4 mg/dL (0.32 to <0.45 mmol/L)	<1.0 mg/dL (<0.32 mmol/L)
Phosphate, low: 1 to 14 years of age	3.0 to <3.5 mg/dL (0.97 to <1.13 mmol/L)	2.5 to <3.0 mg/dL (0.81 to <0.97 mmol/L)	1.5 to <2.5 mg/dL (0.48 to <0.81 mmol/L)	<1.5 mg/dL (<0.48 mmol/L)
Phosphate, low: <1 year of age	3.5 to <4.5 mg/dL (1.13 to <1.45 mmol/L)	2.5 to <3.5 mg/dL (0.81 to <1.13 mmol/L)	1.5 to <2.5 mg/dL (0.48 to <0.81 mmol/L)	<1.5 mg/dL (<0.48 mmol/L)
Potassium, high	5.6 to <6.0 mEq/L or mmol/L	6.0 to <6.5 mEq/L or mmol/L	6.5 to <7.0 mEq/L or mmol/L	≥7.0 mEq/L or mmol/L
Potassium, low	3.0 to <3.4 mEq/L or mmol/L	2.5 to <3.0 mEq/L or mmol/L	2.0 to <2.5 mEq/L or mmol/L	<2.0 mEq/L or mmol/L
Sodium, high	146 to <150 mEq/L or mmol/L	150 to <154 mEq/L or mmol/L	154 to <160 mEq/L or mmol/L	≥160 mEq/L or mmol/L
Sodium, low	130 to <135 mEq/L or mmol/L	125 to <130 mEq/L or mmol/L	121 to <125 mEq/L or mmol/L	<121 mEq/L or mmol/L
Uric acid, high	7.5 to <10.0 mg/dL (0.45 to <0.59 mmol/L)	10.0 to <12.0 mg/dL (0.59 to <0.71 mmol/L)	12.0 to <15.0 mg/dL (0.71 to <0.89 mmol/L)	≥15.0 mg/dL (≥0.89 mmol/L)

LLN=lower limit of normal.

Appendix 10: Division of AIDS (DAIDS) Table for Grading the Severity of Adult and Pediatric Adverse Events

Table 1 Severity Grading for Adult and Pediatric Adverse Events (cont.)

Parameter	Grade 1 (Mild)	Grade 2 (Moderate)	Grade 3 (Severe)	Grade 4 (Potentially Life-Threatening)
Hematology				
Absolute CD4 ⁺ count, low (not HIV infected): >5 years of age	300 to <400 cells/mm ³ (0.300×10^9 to $<0.400 \times 10^9$ cells/L)	200 to <300 cells/mm ³ (0.200×10^9 to $<0.300 \times 10^9$ cells/L)	100 to <200 cells/mm ³ (0.100×10^9 to $<0.200 \times 10^9$ cells/L)	<100 cells/mm ³ (0.100×10^9 cells/L)
Absolute lymphocyte count, low (not HIV infected): >5 years of age	600 to <650 cells/mm ³ (0.600×10^9 to $<0.650 \times 10^9$ cells/L)	500 to <600 cells/mm ³ (0.500×10^9 to $<0.600 \times 10^9$ cells/L)	350 to <500 cells/mm ³ (0.350×10^9 to $<0.500 \times 10^9$ cells/L)	<350 cells/mm ³ ($<0.350 \times 10^9$ cells/L)
Absolute neutrophil count, low: >7 days of age	800 to 1000 cells/mm ³ (0.800×10^9 to 1.000×10^9 cells/L)	600 to 799 cells/mm ³ (0.600×10^9 to 0.799×10^9 cells/L)	400 to 599 cells/mm ³ (0.400×10^9 to 0.599×10^9 cells/L)	<400 cells/mm ³ ($<0.400 \times 10^9$ cells/L)
Absolute neutrophil count, low: 2 to 7 days of age	1250 to 1500 cells/mm ³ (1.250×10^9 to 1.500×10^9 cells/L)	1000 to 1249 cells/mm ³ (1.000×10^9 to 1.249×10^9 cells/L)	750 to 999 cells/mm ³ (0.750×10^9 to 0.999×10^9 cells/L)	<750 cells/mm ³ ($<0.750 \times 10^9$ cells/L)
Absolute neutrophil count, low: ≤1 day of age	4000 to 5000 cells/mm ³ (4.000×10^9 to 5.000×10^9 cells/L)	3000 to 3999 cells/mm ³ (3.000×10^9 to 3.999×10^9 cells/L)	1500 to 2999 cells/mm ³ (1.500×10^9 to 2.999×10^9 cells/L)	<1500 cells/mm ³ ($<1.500 \times 10^9$ cells/L)
Fibrinogen, decreased	100 to <200 mg/dL (1.00 to <2.00 g/L) or 0.75 to <1.00 × LLN	75 to <100 mg/dL (0.75 to <1.00 g/L) or ≥ 0.50 to <0.75 × LLN	50 to <75 mg/dL (0.50 to <0.75 g/L) or 0.25 to <0.50 × LLN	<50 mg/dL (<0.50 g/L) or $<0.25 \times$ LLN or associated with gross bleeding

LLN=lower limit of normal.

Appendix 10: Division of AIDS (DAIDS) Table for Grading the Severity of Adult and Pediatric Adverse Events

Table 1 Severity Grading for Adult and Pediatric Adverse Events (cont.)

Parameter	Grade 1 (Mild)	Grade 2 (Moderate)	Grade 3 (Severe)	Grade 4 (Potentially Life-Threatening)
Hematology (cont.)				
Hemoglobin, low: ≥ 13 years of age (male only) ^k	10.0 to 10.9 g/dL (6.19 to 6.76 mmol/L)	9.0 to <10.0 g/dL (5.57 to <6.19 mmol/L)	7.0 to <9.0 g/dL (4.34 to <5.57 mmol/L)	<7.0 g/dL (<4.34 mmol/L)
Hemoglobin, low: ≥ 13 years of age (female only) ^k	9.5 to 10.4 g/dL (5.88 to 6.48 mmol/L)	8.5 to <9.5 g/dL (5.25 to <5.88 mmol/L)	6.5 to <8.5 g/dL (4.03 to <5.25 mmol/L)	<6.5 g/dL (<4.03 mmol/L)
Hemoglobin, low: 57 days to < 13 years of age (male and female) ^k	9.5 to 10.4 g/dL (5.88 to 6.48 mmol/L)	8.5 to <9.5 g/dL (5.25 to <5.88 mmol/L)	6.5 to <8.5 g/dL (4.03 to <5.25 mmol/L)	<6.5 g/dL (<4.03 mmol/L)
Hemoglobin, low: 36 to 56 days of age (male and female) ^k	8.5 to 9.6 g/dL (5.26 to 5.99 mmol/L)	7.0 to <8.5 g/dL (4.32 to <5.26 mmol/L)	6.0 to <7.0 g/dL (3.72 to <4.32 mmol/L)	<6.0 g/dL (<3.72 mmol/L)
Hemoglobin, low: 22 to 35 days of age (male and female) ^k	9.5 to 11.0 g/dL (5.88 to 6.86 mmol/L)	8.0 to <9.5 g/dL (4.94 to <5.88 mmol/L)	6.7 to <8.0 g/dL (4.15 to <4.94 mmol/L)	<6.7 g/dL (<4.15 mmol/L)
Hemoglobin, low: 8 to 21 days of age (male and female) ^k	11.0 to 13.0 g/dL (6.81 to 8.10 mmol/L)	9.0 to <11.0 g/dL (5.57 to <6.81 mmol/L)	8.0 to <9.0 g/dL (4.96 to <5.57 mmol/L)	<8.0 g/dL (<4.96 mmol/L)
Hemoglobin, low: ≤ 7 days of age (male and female) ^k	13.0 to 14.0 g/dL (8.05 to 8.72 mmol/L)	10.0 to <13.0 g/dL (6.19 to <8.05 mmol/L)	9.0 to <10.0 g/dL (5.59 to <6.19 mmol/L)	<9.0 g/dL (<5.59 mmol/L)

^k Male and female sex are defined as sex at birth. For transgender participants ≥ 13 years of age who have been on hormone therapy for more than 6 consecutive months, hemoglobin grade should be based on values for the gender with which they identify (e.g., grade for a transgender female should be based on hemoglobin laboratory values for females).

Appendix 10: Division of AIDS (DAIDS) Table for Grading the Severity of Adult and Pediatric Adverse Events

Table 1 Severity Grading for Adult and Pediatric Adverse Events (cont.)

Parameter	Grade 1 (Mild)	Grade 2 (Moderate)	Grade 3 (Severe)	Grade 4 (Potentially Life-Threatening)
Hematology (cont.)				
INR, high (not on anticoagulation therapy)	1.1 to $<1.5 \times$ ULN	1.5 to $<2.0 \times$ ULN	2.0 to $<3.0 \times$ ULN	$\geq 3.0 \times$ ULN
Methemoglobin (% hemoglobin)	5.0% to $<10.0\%$	10.0% to $<15.0\%$	15.0% to $<20.0\%$	$\geq 20.0\%$
PTT, high (not on anticoagulation therapy)	1.1 to $<1.66 \times$ ULN	1.66 to $<2.33 \times$ ULN	2.33 to $<3.00 \times$ ULN	$\geq 3.00 \times$ ULN
Platelets, decreased	100,000 to $<125,000$ cells/mm ³ (100.000×10^9 to $<125.000 \times 10^9$ cells/L)	50,000 to $<100,000$ cells/mm ³ (50.000×10^9 to $<100.000 \times 10^9$ cells/L)	25,000 to $<50,000$ cells/mm ³ (25.000×10^9 to $<50.000 \times 10^9$ cells/L)	$<25,000$ cells/mm ³ ($<25.000 \times 10^9$ cells/L)
PT, high (not on anticoagulation therapy)	1.1 to $<1.25 \times$ ULN	1.25 to $<1.50 \times$ ULN	1.50 to $<3.00 \times$ ULN	$\geq 3.00 \times$ ULN
WBC, decreased: > 7 days of age	2000 to 2499 cells/mm ³ (2.000×10^9 to 2.499×10^9 cells/L)	1500 to 1999 cells/mm ³ (1.500×10^9 to 1.999×10^9 cells/L)	1000 to 1499 cells/mm ³ (1.000×10^9 to 1.499×10^9 cells/L)	<1000 cells/mm ³ ($<1.000 \times 10^9$ cells/L)
WBC, decreased: ≤ 7 days of age	5500 to 6999 (5.500×10^9 to 6.999×10^9 cells/L)	4000 to 5499 (4.000×10^9 to 5.499×10^9 cells/L)	2500 to 3999 (2.500×10^9 to 3.999×10^9 cells/L)	<2500 ($<2.500 \times 10^9$ cells/L)

ULN = upper limit of normal.

Appendix 10: Division of AIDS (DAIDS) Table for Grading the Severity of Adult and Pediatric Adverse Events

Table 1 Severity Grading for Adult and Pediatric Adverse Events (cont.)

Parameter	Grade 1 (Mild)	Grade 2 (Moderate)	Grade 3 (Severe)	Grade 4 (Potentially Life-Threatening)
Urinalysis				
Glycosuria (random collection tested by dipstick)	Trace to 1+ or ≤ 250 mg	2+ or > 250 to ≤ 500 mg	$> 2+$ or > 500 mg	—
Hematuria (not to be reported based on dipstick findings or on blood believed to be of menstrual origin)	6 to < 10 RBCs per high power field	≥ 10 RBCs per high power field	Gross, with or without clots or with RBC casts or intervention indicated	Life-threatening consequences
Proteinuria (random collection tested by dipstick)	1+	2+	3+ or higher	—

Appendix 10: Division of AIDS (DAIDS) Table for Grading the Severity of Adult and Pediatric Adverse Events

Table 7 Severity Grading for Elevated Total Bilirubin in Neonates

Parameter	Grade 1 (Mild)	Grade 2 (Moderate)	Grade 3 (Severe)	Grade 4 (Potentially Life-Threatening)
Neonates ≥ 35 Weeks Gestational Age				
<24 hours of age	4 to < 7 mg/dL (68.4 to < 119.7 µmol/L)	7 to < 10 mg/dL (119.7 to < 171 µmol/L)	10 to < 17 mg/dL (171 to < 290.7 µmol/L)	≥ 17 mg/dL (≥ 290.7 µmol/L)
24 to < 48 hours of age	5 to < 8 mg/dL (85.5 to < 136.8 µmol/L)	8 to < 12 mg/dL (136.8 to < 205.2 µmol/L)	12 to < 19 mg/dL (205.2 to < 324.9 µmol/L)	≥ 19 mg/dL (≥ 324.9 µmol/L)
48 to < 72 hours of age	8.5 to < 13 mg/dL (145.35 to < 222.3 µmol/L)	13 to < 15 mg/dL (222.3 to < 256.5 µmol/L)	15 to < 22 mg/dL (256.5 to < 376.2 µmol/L)	≥ 22 mg/dL (≥ 376.2 µmol/L)
72 hours to < 7 days of age	11 to < 16 mg/dL (188.1 to < 273.6 µmol/L)	16 to < 18 mg/dL (273.6 to < 307.8 µmol/L)	18 to < 24 mg/dL (307.8 to < 410.4 µmol/L)	≥ 24 mg/dL (≥ 410.4 µmol/L)
7 to 28 days of age (breast feeding)	5 to < 10 mg/dL (85.5 to < 171 µmol/L)	10 to < 20 mg/dL (171 to < 342 µmol/L)	20 to < 25 mg/dL (342 to < 427.5 µmol/L)	≥ 25 mg/dL (≥ 427.5 µmol/L)
7 to 28 days of age (not breast feeding)	1.1 to < 1.6× ULN	1.6 to < 2.6× ULN	2.6 to < 5.0× ULN	≥ 5.0× ULN

ULN = upper limit of normal.

Appendix 10: Division of AIDS (DAIDS) Table for Grading the Severity of Adult and Pediatric Adverse Events

Table 2 Severity Grading for Elevated Total Bilirubin in Neonates (cont.)

Parameter	Grade 1 (Mild)	Grade 2 (Moderate)	Grade 3 (Severe)	Grade 4 (Potentially Life-Threatening)
Neonates <35 Weeks Gestational Age				
32 to <35 weeks gestational age and < 7 days of age	—	—	10 to < 14 mg/dL (171 to < 239.4 µmol/L)	≥ 14 mg/dL (≥ 239.4 µmol/L)
28 to <32 weeks gestational age and < 7 days of age	—	—	6 to < 10 mg/dL (102.6 to < 171 µmol/L)	≥ 10 mg/dL (≥ 171 µmol/L)
<28 weeks gestational age and < 7 days of age	—	—	5 to < 8 mg/dL (85.5 to < 136.8 µmol/L)	≥ 8 mg/dL (≥ 136.8 µmol/L)
7 to 28 days of age (breast feeding)	5 to < 10 mg/dL (85.5 to < 171 µmol/L)	10 to < 20 mg/dL (171 to < 342 µmol/L)	20 to < 25 mg/dL (342 to < 427.5 µmol/L)	≥ 25 mg/dL (≥ 427.5 µmol/L)
7 to 28 days of age (not breast feeding)	1.1 to < 1.6 × ULN	1.6 to < 2.6 × ULN	2.6 to < 5.0 × ULN	≥ 5.0 × ULN

ULN = upper limit of normal.

Appendix 10: Division of AIDS (DAIDS) Table for Grading the Severity of Adult and Pediatric Adverse Events

Table 3 Severity Grading for Events Not Specifically Listed in Tables 1 and 2

Grade	Severity
1	Mild; transient or mild discomfort (< 48 hours); no medical intervention or therapy required
2	Moderate; mild to moderate limitation in activity; some assistance may be needed; no or minimal medical intervention or therapy required
3	Severe; marked limitation in activity; some assistance usually required; medical intervention or therapy required; hospitalization possible
4	Life-threatening; extreme limitation in activity; significant assistance required; significant medical intervention or therapy required, hospitalization or hospice care probable

REFERENCE

[HHS] U.S. Department of Health and Human Services, National Institutes of Health, National Institute of Allergy and Infectious Diseases, Division of AIDS. Division of AIDS (DAIDS) table for grading the severity of adult and pediatric adverse events, corrected version 2.1 [resource on the Internet]. 2017 [cited: 12 October 2021]. Available from: <https://rsc.niaid.nih.gov/sites/default/files/daidsgradingcorrectedv21.pdf>.

Appendix 11
**Investigational Medicinal Product and Non-Investigational
Medicinal Product Designations (for Use in European Economic
Area and United Kingdom)**

Product Name	IMP/NIMP Designation	Marketing Authorization Status in EEA/and/ /U.K.	Used within Marketing Authorization
GDC-6599	IMP (test product)	Not approved	Not applicable
GDC-6599 Placebo	IMP (Placebo)	Not approved	Not applicable
Mannitol (Aridol®/Osmohale®)	IMP (challenge agent)	Approved	Yes

EEA = European Economic Area; IMP = investigational medicinal product; U.K. = United Kingdom.

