Laboratory testing may be repeated one time during screening if the initial results are outside the normal range specified by the laboratory performing the test or outside the ranges specified above.

- QT interval corrected through use of Fridericia's formula (QTcF) >450 ms

If the initial QTcF >450 ms, the ECG should be repeated at least 30 minutes after the first ECG. The patient may be enrolled if second QTcF ≤ 450 ms.
- History of ventricular dysrhythmias or risk factors for ventricular dysrhythmias such as structural heart disease (e.g., severe left ventricular systolic dysfunction, left ventricular hypertrophy), unstable coronary heart disease (symptomatic or with ischemia demonstrated by diagnostic testing) within last 12 months, clinically significant electrolyte abnormalities, or family history of sudden unexplained death or long QT syndrome
- Current treatment with medications that are well known to prolong the QT interval *within 1 month prior to screening*

Refer to [Appendix 12](#) for a list of drugs associated with QT prolongation.

- If stipulated by local or national laws: employed by the site, the Sponsor, or Sponsor representatives or financially dependent on, or related to, an employee of the site, the Sponsor, or Sponsor representatives
- History or presence of an abnormal ECG that is clinically significant in the investigator's opinion, including complete left bundle branch block, second- or third-degree atrioventricular heart block, or evidence of prior myocardial infarction within last 12 months
- Known allergic sensitivity or reaction to adhesives, such as those used for VitaloJAK chest sensor application, that in the opinion of the investigator may impact the ability of the patient to complete the study

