4.5.11 Electrocardiograms

A single 12-lead ECG will be performed at screening to confirm eligibility. If the initial QTcF >450 ms, the ECG should be repeated at least 30 minutes after the first ECG. The patient may be enrolled if second QTcF ≤450 ms. Thereafter, a single 12-lead ECG recording must be obtained for each specified timepoint. Single 12-lead ECG recordings may also be obtained at unscheduled timepoints. Triplicate ECGs are not required; however, ECGs with artifacts that may interfere with interpretation should be repeated.

All ECG recordings must be performed using a standard high-quality, high-fidelity digital electrocardiograph machine equipped with computer-based interval measurements. Lead placement should be as consistent as possible. ECG recordings must be performed after the patient has been resting in a supine position for at least 10 minutes. All ECGs are to be obtained prior to other procedures scheduled at that same time (e.g., vital sign measurements, blood draws) and should not be obtained within 3 hours after any meal. Circumstances that may induce changes in heart rate, including environmental distractions (e.g., television, radio, conversation) should be avoided during the pre-ECG resting period and during ECG recording.

For safety monitoring purposes, the investigator must review, sign, and date all ECG tracings. Paper copies of ECG tracings will be kept as part of the patient's permanent study file at the site. Digital recordings will be stored at the site. The following should be recorded in the appropriate eCRF: heart rate, RR interval, QRS interval, PR duration, uncorrected QT interval, and QTcF based on the machine readings of the individual ECG tracings. Any morphologic waveform changes or other ECG abnormalities must be documented on the eCRF. If considered appropriate by the Sponsor, ECGs may be analyzed retrospectively at a central laboratory.

If at a particular timepoint the mean QTcF is >500 ms and/or >60 ms longer than the baseline value, another ECG must be recorded, ideally within the next 5 minutes, and

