4.6 TREATMENT, PATIENT, STUDY, AND SITE DISCONTINUATION

4.6.1 Study Treatment Discontinuation

A patient must permanently discontinue study treatment if any of the following criteria are met:

- Any medical condition that the investigator or Sponsor determines may jeopardize the patient's safety if he or she continues to receive study treatment
- Investigator or Sponsor determination that treatment discontinuation is in the best interest of the patient
- Pregnancy
- Serious adverse event related to study drug in the opinion of the investigator and Sponsor
- Clinically significant Grade ≥ 3 adverse event, as determined by the investigator, related to study drug
- Persistent (>2 hours) Grade 1 bleeding
- [REDACTED]
- [REDACTED]
- [REDACTED]
- INR ≥ 4 and Grade 3 or Grade 4 bleeding
- [REDACTED]
- ALT or AST elevation $\geq 3 \times$ ULN in combination with either total bilirubin $\geq 2 \times$ ULN or clinical jaundice (Hy's Law; see Section [5.3.5.6](#))
- Episode of torsades de pointes (unless there is a clear alternative cause for the changes)

- Sustained (at least two ECG measurements > 30 minutes apart) QTcF that is > 500 ms and > 60 ms longer than the baseline value or sustained QTcF > 515 ms (unless there is a clear alternative cause for the changes)
- Patient requirement for a prohibited therapy (see Section 4.4.2)

The IMC will review any event suggestive of a significant safety risk to patients. Study treatment for all enrolled patients may be paused or discontinued pending IMC review if any of the following criteria are met in two or more patients:

- Elevated ALT or AST in combination with either an elevated bilirubin or clinical jaundice as defined by Hy's law (see Section 5.3.5.6)
- Sustained (at least two ECG measurements > 30 minutes apart) QTcF that is > 500 ms and > 60 ms longer than the baseline value or sustained QTcF > 515 ms (unless there is a clear alternative cause for the changes)
- Episode of torsades de pointes (unless there is a clear alternative cause for the changes)

The primary reason for study treatment discontinuation should be documented on the appropriate eCRF. Patients who discontinue study treatment prematurely will not be replaced.

Patients will return to the clinic for a treatment completion or treatment discontinuation [REDACTED] days after the final dose of study drug.

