5.1.3.3 Management of Increases in QT Interval

Study drug should be discontinued in patients who develop any of the following, unless there is a clear alternative cause for the changes:

- Sustained (at least two ECG measurements >30 minutes apart) QTcF that is >500 ms and >60 ms longer than the baseline value
- Sustained absolute QTcF that is >515 ms
- An episode of torsades de pointes or a new ECG finding of clinical concern

Of note, if there is a new intraventricular conduction block, the increase in QRS complex duration should be subtracted from the QTcF change, because this represents an increase in QTcF unrelated to alterations in repolarization. Also of note, it is not uncommon to record arrhythmias such as non-sustained ventricular tachycardia, supraventricular tachycardia, pauses, or atrial fibrillation in healthy volunteers receiving placebo during periods of extended ECG monitoring. Therefore, it is critical that expert cardiology advice be sought to confirm any ECG changes and to ascertain the likelihood of a drug-induced arrhythmia versus the background occurrence of this arrhythmia. In such a situation, saving all available ECG data is highly suggested.

Management of patients with sustained QTcF prolongation should include close monitoring, with ECGs repeated at least hourly until two successive ECGs show resolution of the findings, correction of any electrolyte abnormalities, and possible discontinuation of other concomitant medications that are known to prolong the QT interval. Consultation with a cardiologist or electrophysiologist is recommended, to help in the management of such patients.

In rare circumstances, it may be acceptable to resume study drug, at a lower dose, provided that any ECG abnormalities have resolved and the patient is appropriately monitored. Clinical judgment should be applied.

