5.2.3 Adverse Events of Special Interest (Immediately Reportable to the Sponsor)

Adverse events of special interest are required to be reported by the investigator to the Sponsor immediately (i.e., no more than 24 hours after learning of the event; see Section 5.4.2 for reporting instructions). Adverse events of special interest for this study are as follows:

- [REDACTED]
- Clinically significant Grade ≥ 3 adverse event, as determined by the investigator
- [REDACTED]
 - [REDACTED]
 - [REDACTED]
 - [REDACTED]
- [REDACTED]
- Cases of potential drug-induced liver injury that include an elevated ALT or AST in combination with either an elevated bilirubin or clinical jaundice, as defined by Hy's Law (see Section 5.3.5.6)
- Suspected transmission of an infectious agent by the study drug, as defined below
Any organism, virus, or infectious particle (e.g., prion protein transmitting transmissible spongiform encephalopathy), pathogenic or non-pathogenic, is considered an infectious agent. A transmission of an infectious agent may be suspected from clinical symptoms or laboratory findings that indicate an infection in a patient exposed to a medicinal product. This term applies only when a contamination of the study drug is suspected.

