Heart failure	No symptoms and laboratory or cardiac imaging abnormalities	Symptoms with mild to moderate activity or exertion	Symptoms at rest or with minimal activity or exertion (e.g., hypoxemia) or intervention indicated (e.g., oxygen)	Life-threatening consequences or urgent intervention indicated (e.g., vasoactive medications, ventricular assist device, heart transplant)
Hemorrhage (with significant acute blood loss)	—	Symptoms and no transfusion indicated	Symptoms and transfusion of ≤ 2 units packed RBCs (for children, packed RBCs ≤ 10 cc/kg) indicated	Life-threatening hypotension or transfusion of > 2 units packed RBCs (for children, packed RBCs > 10 cc/kg) indicated
Prolonged PR interval or AV block: > 16 years of age (Report the most appropriate term)	PR interval 0.21 to < 0.25 seconds	PR interval ≥ 0.25 seconds or Type I second-degree AV block	Type II second-degree AV block or ventricular pause ≥ 3.0 seconds	Complete AV block
Prolonged PR interval or AV block: ≤ 16 years of age (Report the most appropriate term)	First-degree AV block (PR interval $>$ normal for age and rate)	Type I second-degree AV block	Type II second-degree AV block or ventricular pause ≥ 3.0 seconds	Complete AV block
Prolonged QTc interval (corrected per Bazett's formula)	0.45 to 0.47 seconds	> 0.47 to 0.50 seconds	> 0.50 seconds or ≥ 0.06 seconds above baseline	Life-threatening consequences (e.g., torsade de pointes, other associated serious ventricular dysrhythmia)

AV = atrioventricular.

Parameter	Grade 1 (Mild)	Grade 2 (Moderate)	Grade 3 (Severe)	Grade 4 (Potentially Life-Threatening)
-----------	-------------------	-----------------------	---------------------	---

Appendix 10: Division of AIDS (DAIDS) Table for Grading the Severity of Adult and Pediatric Adverse Events

Table 1 Severity Grading for Adult and Pediatric Adverse Events (cont.)

Cardiovascular (cont.)				
Thrombosis or embolism (Report the most appropriate term)	—	Symptoms and no intervention indicated	Symptoms and intervention indicated	Life-threatening embolic event (e.g., pulmonary embolism, thrombus)
Dermatologic				
Alopecia (scalp only)	Detectable by study participant, caregiver, or physician and causing no or minimal interference with usual social and functional activities	Obvious on visual inspection and causing greater than minimal interference with usual social and functional activities	—	—

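### Appendix 10 grades reported QTc prolongation by Bazett while the protocol's other QT rules use Fridericia, so a QT event's grade depends on heart rate and can disagree with the QTcF alert

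*Combined protocol and SAP*

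**What the plan says.** Section 5.3.3 and the introduction to Appendix 10 tell the investigator to grade the severity of reported adverse events with the DAIDS table, lightly adapted by the sponsor. The cardiovascular part of Table 1 in Appendix 10 has a row headed "Prolonged QTc interval (corrected per Bazett's formula"). Its bands are 0.45 to 0.47 s (Grade 1), above 0.47 to 0.50 s (Grade 2), and above 0.50 s or "≥ 0.06 seconds above baseline" (Grade 3).

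The other QT rules that name a correction all use Fridericia:

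- Section 4.1.2 (entry): patients are excluded for "QT interval corrected through use of Fridericia's formula (QTcF) >450 ms".
- Section 4.5.11 (data captured): the eCRF takes heart rate, RR, "uncorrected QT interval, and QTcF based on the machine readings of the individual ECG tracings".
- Section 4.5.11 (repeat-ECG alert): another ECG is required when "mean QTcF is >500 ms and/or >60 ms longer than the baseline value".
- Section 4.6.1 (stopping one patient, and the study-wide pause): a sustained "QTcF that is > 500 ms and > 60 ms longer than the baseline value or sustained QTcF > 515 ms".
- Section 5.1.3.3 (QT management): the same sustained criteria, including "Sustained absolute QTcF that is >515 ms".

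Severity by the DAIDS scale is a safety endpoint in Section 2, Table 1, and Section 6.5 summarizes adverse events by grade. Section 5.2.3 makes a "Clinically significant Grade ≥ 3 adverse event, as determined by the investigator" an event of special interest. Section 4.6.1 stops treatment for such an event if it is also drug-related.

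**The concern.** Two corrections are in force for the same ECG, and no text says how they relate. The grading table asks for a Bazett value that no one is assigned to derive, while the investigator has a QTcF from the machine. One investigator may compute Bazett as written and another may grade on the QTcF in front of them. If both follow the table, the grade still depends on heart rate as well as on QTcF.

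The clearest clash is with the repeat-ECG alert. The alert and Grade 3 have nearly the same numbers and the same either/or logic (500 ms, 60 ms over baseline), but each is applied to a different quantity. At stake is whether the severity of a reported QT event means the same thing as the rest of the QT monitoring. That feeds the adverse event severity summaries, special-interest reporting, and one route to discontinuation.

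**Working it through.** The plan states no figure on this point, so there is none to reproduce.

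**Inputs.** The grade bands come from Appendix 10 and the alert from Section 4.5.11. Heart rates and QTcF values below are assumptions, because the documents give none.

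**Relation between the corrections.** With RR = 60/HR in seconds, QTcB = QT/RR^(1/2) and QTcF = QT/RR^(1/3). Dividing gives QTcB = QTcF × (HR/60)^(1/6).

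| HR (bpm) | QTcB/QTcF |
|---|---|
| 50 | 0.9701 |
| 60 | 1.0000 |
| 70 | 1.0260 |
| 80 | 1.0491 |
| 90 | 1.0699 |

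**Absolute bands only.** A QTcF of 480 ms is 465.6 ms by Bazett at 50 bpm (Grade 1), 480.0 ms at 60 bpm (Grade 2) and 503.6 ms at 80 bpm (Grade 3). It passes 500 ms at 60 × (500/480)^6 = 76.7 bpm. Graded on QTcF, it would be Grade 2 at every heart rate.

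**Grade 3 without an alert.** QTcF goes from 420 ms at 60 bpm to 450 ms at 90 bpm.
- QTcF: 450 − 420 = +30 ms, so no alert; on QTcF this would be Grade 1.
- Bazett: 450 × 1.0699 = 481.5 ms, and 481.5 − 420.0 = +61.5 ms, which is Grade 3.
- With these QTcF values, the Bazett rise reaches 60 ms once follow-up heart rate is 60 × (480/450)^6 = 88.4 bpm.

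**Alert without Grade 3.** QTcF goes from 400 ms at 80 bpm to 465 ms at 60 bpm.
- QTcF: 465 − 400 = +65 ms, so the alert is met; on QTcF this would be Grade 3.
- Bazett: the baseline is 400 × 1.0491 = 419.6 ms, and 465.0 − 419.6 = +45.4 ms. The absolute value is 465 ms, so this is Grade 1.

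**Heart rate unchanged.** The change from baseline then differs between corrections only by the factor in the table, from 0.970 at 50 bpm to 1.070 at 90 bpm. Disagreement on the absolute bands remains.

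**The case against.** The strongest case on the other side is that little depends on this row, and most of that case stands.

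- **Few ECGs are graded.** Appendix 10 applies to reported adverse events, not to every tracing. Section 5.2.1 counts an ECG deterioration when it brings symptoms or a treatment change, although its first item, any unfavourable sign, is wider. Section 5.3.5.8 counts a preexisting condition only if it worsens. A reader might infer that a patient entering at the QTcF limit of 450 ms would be graded differently by heart rate. An unchanged, asymptomatic entry value would not ordinarily be reported, so that inference carries little weight.
- **QT safety rules do not use the grade.** A reader might infer that the mismatch weakens patient protection. It does not: the repeat ECG, Medical Monitor notification, stopping and study pause all work from QTcF. The Grade 3 routes also need a finding of clinical significance and, for discontinuation, drug-relatedness.
- **The Bazett value can be obtained.** A reader might infer that the grade cannot be computed because the eCRF lists no QTcB. QT and RR are both recorded, so it can be derived.
- **The displays are not committed to this row.** Section 6.5 promises grades on ECG displays only where appropriate, and Section 2 lists no ECG-change endpoint.
- **The change-from-baseline examples need large shifts in resting heart rate** (60 to 90 bpm, 80 to 60 bpm), and ECGs follow at least 10 minutes of supine rest. This is fair; such shifts will not be typical.
- **The table is a published scale, and a grade need not equal an alert.** This is partly right. However, the protocol already adapts the table to the sponsor's conventions, and a difference in purpose does not explain a different heart-rate correction.

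**Conclusion.** The inconsistency is real and the impact is minor. The grade of a reported QT event depends on heart rate and can disagree in both directions with the near-identical QTcF alert. The sizes shown (+30 against +61.5 ms, and +65 against +45.4 ms) follow from the two formulas, but they rest on assumed heart rates and QTcF values. The documents give no basis for saying how often such cases would occur.

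The effect is confined to the severity assigned to QT adverse events and to what follows from that grade subject to investigator judgement. Efficacy and the QT-specific alert, stopping and pause rules are untouched. This is a cheap improvement in consistency, not a flaw that threatens the study's conclusions.

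**What to change.** In the QTc row of Appendix 10, Table 1, replace Bazett's formula with Fridericia's formula (QTcF) and keep the cut-offs. The Grade 3 thresholds then match the repeat-ECG alert except at a rise of exactly 60 ms. Grade and stopping rule will still differ, because stopping needs a sustained value and either both limits exceeded or QTcF above 515 ms.

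The change is one table cell, and QTcF is already recorded. The downsides to state are:

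- It is one more departure from the standard DAIDS table.
- Above 60 bpm the absolute limits become harder to reach. Bazett 500 ms corresponds to QTcF 500/1.0260 = 487.3 ms at 70 bpm and 500/1.0491 = 476.6 ms at 80 bpm, so some events now Grade 3 would fall to Grade 2. Below 60 bpm the limits become easier to reach.
- The 470 ms boundary between Grades 1 and 2 is carried over, although the protocol applies it to QTcF nowhere else. The 450, 500 and 60 ms values are already used with QTcF.
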